## **7.4 Follow up for Adverse Events**

For non-serious adverse events, participants will be contacted to see how they are doing. They will be followed until any adverse events, at least possibly related to the study are resolved. The GH IRB will offer guidance about follow-up required for other conditions unrelated to the study.

## **7.5 Safety Monitoring**

This is an unmasked Phase trial comparing Enhanced Tai Chi and Usual Medical Care for chronic back pain. Given the favorable safety profile from previous studies of Tai Chi including [name] coupled with the small numbers of adverse events reported in the literature, we propose that this trial will be monitored for safety by an Independent Monitoring Committee. The IMC was established with NCCIH's approval, and consists of a primary care physician, a biostatistician and a Tai Chi instructor.

The IMCs job will be to evaluate the adverse-experience data we will provide them on a regular basis to protect the safety of the study participants. Based on the observed adverse effects of the treatment under study, the IMC will make recommendations on a regular basis to the PI and the Office of Clinical and Regulatory Affairs at the National Center for Complementary and Integrative Health (NCCIH) regarding continuation, termination, or other modifications of the trial.

## **8. INTERVENTION DISCONTINUATION**

There are a variety of conceivable reasons participants may prematurely discontinue the class series and study staff will use the following groupings to categorize them:

- Practice of Tai Chi associated with unacceptable or serious adverse events from perspective of participant
- Continued participation considered inadvisable by investigator, class instructor or participant's physician due to concerns that continued participation poses an unacceptable risk to the patient.
- Participants do not care for the class environment
- Tai Chi perceived as ineffective by participant
- Events in participant's life unrelated to trial (e.g., illness or death in family)
- The study is stopped by the GH IRB, the NCCIH or the OHRP

A study withdrawal form will be completed for individual who discontinues the intervention. In all cases, participants who discontinue treatments will be encouraged to complete the remaining follow-up assessments using the regular follow-up schedule (i.e., 12, 26, and 52 weeks).

## **9. STATISTICAL CONSIDERATIONS**

### **9.1 General Design Issues**

In this feasibility study, we chose a parallel group design using three arms (Enhanced Tai Chi, Comprehensive Health Education Control and Usual Medical Care)

that would be part of a 3 or 4-arm full-scale RCT if an assessment indicates that the larger study is feasible.

By assembling information from interviews with study participants, the Tai Chi instructor, members of the research team, and from study records, we will be able to perform a thorough evaluation of our study procedures and protocols. This evaluation will be guided by the criteria for assessing the adequacy of specific study components clearly specified in the Administrative Year. This information will allow evaluation of the overall feasibility of conducting a large RCT, the size of the pool of potential participants required (and therefore the number of study sites), the feasibility of including the maintenance Tai Chi intervention, and the adequacy of recruitment and follow-up procedures. Finally, this trial will provide estimates of the baseline means and standard deviations of the primary outcome measures, albeit with small sample sizes. If this evaluation concludes that conducting a full-scale RCT of Tai Chi for older adults with cLBP is feasible, this study will provide the information necessary for preparing a grant proposal for successfully conducting such a RCT.

## **9.2 Sample Size and Randomization**

Because this is a feasibility study, the sample size is not designed to detect clinically important effects of the primary effectiveness outcomes, back-related dysfunction and pain intensity. Rather, for this type of study, the sample size needs to be large enough to provide a high likelihood of surfacing any important problems that may exist in the study execution. Our sample size of 78 was chosen based on practical considerations to provide ample opportunity to identify problems with the study procedures, intervention protocols (including adherence), outcome measures, and follow-up rates. Therefore, a trial of this size is insufficiently powered to detect clinically important effects in our outcomes; for example the power would be only 48% assuming a 10% loss to follow-up,  $\alpha=0.05$  and an effect size of 0.5 (similar to a clinically important difference on the RMDQ in younger adults). However, we believe that our proposed sample size is sufficient to determine whether the trial is feasible.

If we conclude that a full-scale RCT of Tai Chi for cLBP in older adults is feasible, we would calculate our sample size requirements using estimates of the standard deviations from large previous RCTs of other CIM interventions of older adults, accepted criteria for the minimum clinically important difference for the RMDQ (our primary outcome measure, which would be measured as a continuous variable), standard levels of type I ( $\alpha=0.05$ ) and type II ( $\beta$  between 0.1 and 0.2, for power between 80% ad 90%) errors, and dropout rates and missing data rates estimated from this study's follow-up rates. If appropriate, the contemporary "best practice" method of imputation for missing data (e.g., multiple imputation) would be used.

Participants would be randomized to each of the three study arms (Enhanced Tai Chi, Comprehensive Health Education and Usual Medical Care). Our study biostatistician would prepare a computer-generated sequence of random numbers that will be inserted into a special computer program for randomization. The program will contain blocks of varying sizes to ensure balanced but unpredictable assignment of participants to both groups. We will consider whether we should conduct randomization

stratified by age (65-79; 80+) and gender because both are related to baseline measures of back dysfunction and pain. If we decide to do this, we would incorporate a stratified randomization scheme into the computer program. We are experienced with both methods of randomizing participants. Further details related to randomization were provided in section 4.4.

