**Figure: Anticipated Design of Full-scale Trial**

### **3. STUDY DESIGN**

The feasibility study will be a three arm parallel group RCT comparing Enhanced Tai Chi to Comprehensive Health Education (Attention Control) to Usual Medical Care in older adults (65 years and older) with cLBP. We plan to recruit 78 community-dwelling, older adults from Kaiser Permanente Washington, an integrated healthcare system with a large population of Medicare enrollees and from the general population as necessary. We will randomize eligible and willing individuals in a 8:3:5 ratio to Enhanced Tai Chi (n=39), Attention Control (n=15) and Usual Medical Care (n=24) using a computer with a tamperproof program that is not predictable in advance. Participants in the Enhanced Tai Chi will receive 36 weeks of classes (which will be 60 minute classes for 2x/week for 12 weeks; followed by a maintenance schedule of 60 minutes classes 1x/week for 6 weeks, then 60 minute classes every 2 weeks for 6 weeks and then 60 minute classes every 4 weeks for 12 weeks. Participants will be asked to practice at home for 15 minutes on every non-class day. They will be provided with YouTube video access (and, if desired, DVDs), and handouts to assist with this.). All classes will be taught in a Kaiser Permanente Washington classroom. Data on adherence to Tai Chi classes and home practice will be collected during the classes themselves. Because Tai Chi will be taught as a series of progressive classes, participants will be recruited in two cohorts of 32 each; each class of Tai Chi will consist of 16 participants.

Outcome assessments will be collected at baseline, 12, 26, and 52 week during in-person visits. Outcome assessors will be unaware of any participant's study groups,

but participants will be asked to complete their own questionnaires. They will either complete them on paper forms or using a tablet computer designed to minimize errors.

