Study staff will randomize each individual to their treatment group using a computer program, accessible by a laptop, designed to ensure that treatment allocation cannot be changed after randomization and cannot be viewed in advance. Our biostatistician will provide our study programmer with a computer-generated sequence of random numbers that will be then inserted into the computer program. Physical assessments and randomization will be carried out in a private space adjacent to the group visit room. Participants will be randomized in blocks of varying size to ensure balanced but unpredictable assignment of participants to both groups. Participants randomized to Tai Chi will be provided information about the time and location of the first class. This process, modified as necessary for older adults, will be repeated to assemble two consecutive recruitment cohorts of 32 participants. In the first cohort, 19 participants will be randomized to Enhanced Tai Chi protocol and 19 to Usual Medical Care. In the second cohort, 20 participants will be randomized to Enhanced Tai Chi protocol, 15 to the Comprehensive Health Education Classes (AC Group), and 5 to Usual Care. The advice from our patient partners, our team members with experience conducting studies of physical activity in older adults and the experience we gain enrolling participants in our small Tai Chi study this summer, will help ensure that our standard recruitment procedures are modified appropriately for this new study population. We will consider whether we should conduct randomization stratified by age (65-79; 80+) and gender because both are related to baseline measures of back dysfunction and pain.

In our large randomized trial of acupuncture for cLBP, we found no differences in the baseline characteristics of participants recruited through mailings and through advertisements in the health plan's quarterly magazine.

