**February, 21st, 2017**

## **Sample Size and Randomization**

Because this is a feasibility study, the sample size is not designed to detect clinically important effects of the primary effectiveness outcomes, back-related dysfunction and pain intensity. Rather, for this type of study, the sample size needs to be large enough to provide a high likelihood of surfacing any important problems that may exist in the study execution. Our sample size of 64 was chosen based on practical considerations to provide ample opportunity to identify problems with the study procedures, intervention protocols (including adherence), outcome measures, and follow-up rates. Therefore, a trial of this size is insufficiently powered to detect clinically important effects in our outcomes. However, we believe that our proposed sample size is sufficient to determine whether the trial is feasible.

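### The 48% power in section 9.2 is under-specified and not met by any pairwise contrast of 39/15/24 if two-sided and unadjusted; cohorts of 32 and the SAP's N of 64 conflict with 78

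*Protocol*

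**What the plan says.** **Power.** Protocol section 9.2 opens its justification with "Our sample size of 78 was chosen based on practical considerations". It then illustrates the lack of power for effectiveness: "the power would be only 48% assuming a 10% loss to follow-up", alpha 0.05 and a standardised effect of 0.5. The sentence does not say which arms are compared, by what test, one- or two-sided, or with what covariates. Section 9.6iii plans a GEE model adjusted for baseline value, gender and age, with Usual Medical Care as referent, but the 48% is not tied to that model and no baseline-outcome correlation is given.

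**Sample size.** The Precis and section 3 give 39 Tai Chi, 15 Attention Control and 24 Usual Medical Care. Section 3 says "We plan to recruit 78 community-dwelling, older adults from Kaiser Permanente Washington" and, later in the same paragraph, "participants will be recruited in two cohorts of 32 each; each class of Tai Chi will consist of 16 participants". Section 4.4 says the process will be "repeated to assemble two consecutive recruitment cohorts of 32 participants", then gives the arm counts: "In the first cohort, 19 participants will be randomized to Enhanced Tai Chi protocol and 19 to Usual Medical Care", and "In the second cohort, 20 participants will be randomized to Enhanced Tai Chi protocol" with 15 to Attention Control and 5 to Usual Medical Care. The Precis gives cohorts of 38 and 40. The SAP, dated February 2017, says "Our sample size of 64 was chosen based on practical considerations" and gives no power figure. The protocol is dated July 2017.

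**The concern.** A power figure for a three-arm trial with unequal allocation means something only when the contrast is named. Here the three possible pairs differ by some 15 percentage points, so a reader cannot tell what the 48% describes or check it. The figure also sits beside text that still describes a 64-person trial, which raises the question of which design it belongs to.

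Little is at stake for the trial's conclusions, because section 9.2 uses the figure only to show that effectiveness cannot be tested. The cohort and class numbers matter somewhat more in practice. Recruitment of a class cohort is itself a feasibility outcome in the Precis, so the plan should give one target per cohort.

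**Working it through.** **Inputs.** From section 9.2: d = 0.5, alpha = 0.05, 10% loss. From the Precis and section 3: arms of 39, 15 and 24. Assumed, because the documents do not say: two-sided test, no covariate adjustment, cohorts pooled.

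**Formula.** The noncentrality is λ = d × √[n1·n2/(n1+n2)]. Normal-approximation power is about Φ(λ − 1.96). The t version uses the noncentral t with n1+n2−2 degrees of freedom. Loss is applied as 0.9n, giving 35.1, 13.5 and 21.6.

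**Attempt to reproduce 48% from the current design.** For Tai Chi v Usual Medical Care, λ = 0.5 × √(35.1 × 21.6 / 56.7) = 1.828 and Φ(1.828 − 1.96) = 0.448.

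| Contrast | n after loss | λ | Power, t | Power, normal |
|---|---|---|---|---|
| Tai Chi v Usual Medical Care | 35.1 v 21.6 | 1.828 | 43.5% | 44.8% |
| Tai Chi v Attention Control | 35.1 v 13.5 | 1.561 | 33.4% | 34.5% |
| Attention Control v Usual Medical Care | 13.5 v 21.6 | 1.441 | 28.8% | 30.2% |

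With whole persons (35 or 36 v 21 or 22), the first contrast runs from 42.8% to 45.5%, which is 2.5 to 5.2 points below 48%. Rounding moves the other two by about one point. No pair reaches 48%.

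**Readings that come close** (t / normal):

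1. A 64-person 1:1 trial with 10% loss: 28.8 per arm gives 46.2% / 47.5%, and 29 per arm gives 46.5% / 47.8%.
2. Tai Chi v Usual Medical Care with the loss not applied: 39 v 24, λ = 1.927, 47.5% / 48.7%.
3. Tai Chi v Usual Medical Care with 10% loss and baseline adjustment, using d/√(1−r²). At r = 0.3 this is 46.9% / 48.3%. Power of exactly 48% needs r = 0.34 (t) or 0.29 (normal). The correlation is an assumption.
4. Tai Chi and Attention Control pooled v Usual Medical Care: 48.6 v 21.6, 47.9% / 48.9%. This is not a planned contrast.
5. One-sided Tai Chi v Attention Control: 45.8% / 46.7%.

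Reading 1 is not this design, reading 2 omits the loss that the sentence names, and reading 3 needs an input that the sentence does not give. Readings 4 and 5 need a contrast or a sidedness that it does not state.

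**Sample-size reconciliation.**

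| Source | Cohort 1 | Cohort 2 | Total |
|---|---|---|---|
| Precis | 38 | 40 | 78 |
| Section 4.4, arm counts | 19+19 = 38 | 20+15+5 = 40 | 78 |
| Section 3 and section 4.4, cohort statement | 32 | 32 | 64 |
| SAP | not given | not given | 64 |

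By arm, section 4.4 gives Tai Chi 19+20 = 39, Usual Medical Care 19+5 = 24 and Attention Control 15, which agrees with the Precis. The SAP is 14 below the protocol (14/78 = 18%). Section 3's Tai Chi class of 16 stands against 19 and 20 assigned. The documents do not say whether each cohort forms one class.

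**The case against.** The strongest reply is that no arithmetic error has been shown. Two-sidedness and the absence of adjustment are assumptions made here; section 9.2 states neither. The analysis actually planned in section 9.6iii adjusts for baseline, and with a modest correlation of about 0.3 the current design gives roughly 48% for Tai Chi v Usual Medical Care. This stands. It means the figure is under-specified rather than shown to be wrong. It also means that an unadjusted 44% is no closer to the planned analysis than 48%, so any replacement must carry its conditions.

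A reader might infer that the 48% was carried over from a 64-person two-arm design, since 32 v 32 with 10% loss comes close and the text still speaks of cohorts of 32. The documents do not establish this. The no-loss and baseline-adjusted readings of the current design match as well, and the SAP, which states 64, has no power figure.

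It can also be said that the SAP's 64 is version lag, given its earlier date, and that nothing in the SAP's descriptive analyses depends on it. That is plausible, and the class of 16 may be a leftover of the same kind. But the cohorts of 32 stand in the current protocol beside its own 38 and 40, so version lag in the SAP does not remove the conflict.

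Finally, the protocol says that N was set on practical grounds and disclaims effectiveness hypotheses. That is correct, and it limits the weight of the point.

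**Conclusion.** The point holds and is minor. The protocol's one power figure for this trial cannot be checked as written. Under a two-sided unadjusted test with 10% loss, the nearest pairwise contrast falls about 2.5 to 5.2 points short of it. That gap rests on the assumed test. Under baseline adjustment with an unstated correlation near 0.3 it closes, so the supportable finding is a missing specification and not a proven miscalculation.

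The conflicts in cohort size, class size and total N need no assumption; they can be read directly from the text. A reader might take the SAP's 64 to mean that the intended enrolment is in doubt. The documents do not support that: the Precis, section 3's arm sizes, section 4.4's arm counts and section 9.2 all agree on 78.

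Power is below 50% for every pair of arms on the stated inputs, so the statement that the trial is underpowered for effectiveness stands. No feasibility criterion, planned analysis or enrolment number is affected.

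**What to change.** - **Section 9.2:** delete the 48%, which the argument does not need, or restate it for a named contrast, test, sidedness and adjustment. For Tai Chi v Usual Medical Care, two-sided, unadjusted, with 10% loss, it is about 44%. If a baseline-adjusted figure is preferred, state the assumed correlation.
- **SAP:** change N from 64 to 78 (39/15/24).
- **Sections 3 and 4.4:** change the two cohorts of 32 to 38 and 40.
- **Section 3:** reconcile the Tai Chi class size of 16 with the 19 and 20 assigned in section 4.4, and say whether each cohort is one class.

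The cost is text edits to the two documents. If the power figure is kept, the unadjusted illustration is a few points lower.

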### **9.3 Definition of Populations**

In a full-scale trial, we would perform an intention to treat analysis. Therefore we would include all participants who were randomized into the trial, regardless of whether they participated in the assigned treatments. By using this approach, we would minimize biases that often occur when participants who do not receive the assigned treatments are excluded from analysis. In the full-scale trial, we would also perform a per protocol analysis that included only individuals who adhered to the Tai Chi class protocol, using a threshold that we will determine in our Administrative Year.

### **9.4 Interim Analyses and Stopping Rules**

We are not planning any interim analyses for this feasibility study.

The trial will be stopped only if the Safety Monitoring Body (SMB), the KPW IRB, the NCCIH or the OHRP believes there is an unacceptable risk of serious adverse events in the Tai Chi treatment arm. In this case, the SMB could decide to terminate the entire trial. Based on our previous research and on the small number of reports of adverse events from these treatments reported in the literature, we believe the risk of Serious Adverse Events related to our Tai Chi intervention is quite small, having never been documented in the literature. We are not planning to stop the study for slow accrual or high losses to follow-up because in this feasibility study, we would make changes in recruitment and follow-up procedures to try to maximize the feasibility of the study. We would therefore consider difficulties in these areas as signals that changes in our proposed methods are necessary.

### **9.5 Outcomes**

Our feasibility outcomes will include the information we would report participant flow in the feasibility RCT according to the CONSORT guidelines. This will include collect information on the outcomes at every stage of our recruitment, randomization, and treatment process and follow-up time periods. Many of these outcomes will be collected directed by computer, while others will first be collected with paper forms and then transferred to our database.

At the baseline and 12, 26, and 52-week follow-up study visits, outcome measures and physical assessments will be collected as described in Table 3 (section 6.2.4). The primary outcome measures in the full-scale trial would be back-related function (Roland Morris Disability Questionnaire) and back pain intensity. Further details on these measures are provided in Section 6.2.4.

### **9.6 Data Analyses**

#### **i. Feasibility of a full-scale RCT**

We will use descriptive analyses to examine many aspects of feasibility, including recruitment, randomization, Tai Chi adherence, adverse events and follow-up rates. To assess recruitment feasibility, we will collect information at every stage of our recruitment and randomization process. We will compute the rates of screening and enrollment per month. This will let us know how many invitation letters we would need to send to potentially eligible persons to meet recruitment goals in a large RCT. Our primary method of recruitment will be through mailed invitations to persons meeting our initial inclusion and exclusion criteria according to the information in the EMR (see sections 4.2 and 4.3). This recruitment method will allow us to calculate the percentage of these potentially eligible persons who end up agreeing to participate in the trial. Because ICD codes do not distinguish between chronic and acute pain and do not always distinguish between pain in the lumbar spine (low back) from pain in mid-back or neck, most potentially-eligible persons will be found during screening interviews to not have cLBP. This information will help determine the number of recruitment sites that would be necessary to conduct an adequately-powered RCT. If our primary recruitment method proves inadequate for efficiently meeting our goals, we will evaluate the ability of alternative methods determined in the Administrative Year (e.g., advertising in the health plan's quarterly magazine) to accrue significant numbers of additional participants.

To assess RCT retention rates, we will compute the treatment specific retention rates, which are typically large in our trials. For Tai Chi treatment adherence, we will compute the number of classes attended and the amount of home practice per week. Benchmarks for Tai Chi adherence will be derived (in the Administrative Year) by a thorough literature review of adherence in RCTS evaluating exercise for cLBP, Tai Chi for chronic pain and Tai Chi in the elderly. Additional information, such as ratings of how well participants perform key aspects of the Tai Chi protocol, will be obtained.

To assess safety, we will compute the proportion of persons reporting adverse events as well as the type and seriousness of the event. In our prior studies, 15 to 29% of participants reported mild transient increases in pain when stretching or doing yoga. We think adverse events for Tai Chi may be similarly mild, but slightly less common because of the nature of the movement.

To assess follow-up rates, we will compute treatment specific and overall follow-up rates at each time point. While our prior trials have consistently had post-treatment follow-up rates over 90% in the short term and close to that at one-year follow-ups, we will consider follow-up rates of 80% or better to indicate feasibility.

As described in Section 6.2.4iii, we will obtain qualitative feedback on all aspects of the study from 30 participants. Our prior experience suggests this number is sufficient to elicit a broad range of experience and to begin to see themes and experiences repeated across respondents (i.e., achieve "response saturation"). [name], an experienced qualitative researcher, will conduct these discussion groups, which will be audio recorded and transcribed. We will also invite suggestions for improvement in the study procedures and protocols. Because these debriefing interviews will inquire

about specific experiences and suggestions for improving our procedures and protocols, our analyses will be largely descriptive and not require resource-intensive ethnographic analysis techniques.

